Vapotherm's humidification system is specifically designed to tolerate a high back pressure in the humidification cartridge that is generated by passing these flow rates through small bore cannulae that result in the appropriate flow velocities (turbulent energy).⁸ Since 2000, Vapotherm HVNI has been used extensively and has been well studied and the clinical impact of this ventilation effect using Vapotherm's conventional cannula line is well described^{6-8,13,14,6-8,13,14}. A multi-center recent randomized clinical trial also demonstrated the noninferiority of HVNI to NIPPV in the treatment of undifferentiated respiratory distress for patients presenting to the Emergency Department.² To this day trials have supported HFOT at home in patients with COPD. Low Flow Oxygen Therapy (LFOT) is not enough for COPD patients to have a safe at home stay. In these patients HFOT has been shown to be a valuable option to decrease work of breathing and improve dyspnea. In a retrospective study it was found that HFOT is a capable technology in the home and post-acute rehab facilities to maintain patients with end stage hypoxic lung disease. As Vapotherm leads the innovation of new cannulae for the purpose of HVNI, to provide increased patient comfort, we also seek to evaluate a new device equivalent to Precision Flow technology that will impact ventilatory work effort on dyspneic patients in the home. The goal of the current study is to evaluate Precision

Vapotherm, Inc
New HVNI Device Design Efficacy in Relieving Dyspnea
Confidential

Flow HVNI to HVT2.0 HVNI in a head to head randomized control trial of severely hypercapneic inpatients and outpatients requiring ventilation support.

Vapotherm, Inc
New HVNI Device Design Efficacy in Relieving Dyspnea
Confidential

II. Overall Study Objective

The **overall objective** of this study is to evaluate the ability of HVT2.0, a new HVNI device to improve ventilation, dyspnea and related physiological responses relative to the conventional Precision Flow device design.

The **hypothesis** is that the HVT2.0 device that provides HVNI will deliver comparable ventilation and relief of patient dyspnea, when compared to the Precision Flow device in an inpatient or outpatient hospital setting.

To test this hypothesis, the study will be conducted with the following specific aims:

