Aim #1: Primary Outcome. The primary endpoint is the patient's targeted relief of dyspnea, as measured by the modified Borg (rated perceived dyspnea [RPD]) for each device design tested.

Aim #2: Secondary Outcomes. The secondary endpoints evaluate the patient vital signs (heart rate [HR], respiratory rate [RR], blood pressure [BP]), arterial oxygen saturation (SpO₂), and PCO₂ as measured by a transcutaneous CO₂ device (TcPCO₂). These measurements will be compiled and compared for each device design tested.

Aim #3: Tertiary Outcomes. The tertiary endpoints evaluate the patient and clinician assessment scores. For the patient perception/satisfaction these include: (1) relief of symptoms, and (2) comfort/tolerance. For the clinician perceptions these include: (1) technical/clinical difficulties, (2) patient comfort & tolerance, (3) ease of use, (4) monitoring & support for therapy, and (5) expected/perceived patient outcomes.

The **endpoints** described will establish equivalence of outcomes between Precision Flow HVNI and HVT2.0 HVNI device design.

Vapotherm, Inc

New HVNI Device Design Efficacy in Relieving Dyspnea

Confidential

III. Subject Selection

Subjects will be identified through the use of patient medical records and recruited by study investigators. The study will take place in an inpatient or outpatient setting capable of supporting patients presenting with hypercapnic respiratory failure. Device testing during this study will be performed under the direct supervision of qualified healthcare professionals and appropriately trained study staff to maintain patient safety. The ~~test~~-study will evaluate patient dyspnea, vital signs, ventilation, and oxygenation for each device design tested. Initial patient contact will be made by study investigators. Participants may decide whether to enroll after being consented; furthermore, participants may choose to withdraw their consent at any point throughout the study.

Inclusion Criteria

1. Adults, 18 years or older
2. Demonstrated dyspnea at baseline, established by clinician OR patient assessment (see below)
 - a. Borg Rated Perceived Dyspnea (scale 0-10) of 3 or higher
3. Severe patient baseline hypercarbia/hypercapnia of 50mmHg or higher as measured by TcCo2 or arterial or venous blood gas

Exclusion Criteria

1. Patient has unstable cardiovascular condition
2. Significant nasal occlusion either unilateral or bilateral
3. Inability to provide informed consent
4. Pregnancy

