This sample size was estimated through use of references that (1) approximated minimal clinical important difference of dyspnea (modified Borg scale) and (2) approximated expected standard deviation of prior datasets measuring dyspnea.¹⁶⁻¹⁸ Estimated minimal clinical important difference of dyspnea was determined to be a difference value of 2 in modified Borg for dyspnea.¹⁶ In reviewing publications from Roca 2010 and Schwabbauer 2014, it was estimated that a value of 2 to 3 was suitable for the standard deviation of dyspnea for the modified Borg scale. Therefore, for this study, using the paired t-test sample size calculation, with an expected difference of 2, and an expected standard deviation of 3, using a desired power of 90% with alpha=0.05, the sample size is estimated at 26 to show if the data may or may not have any difference.

Vapotherm, Inc

New HVNI Device Design Efficacy in Relieving Dyspnea

Confidential

VI. Study Procedures

This validation study is non-blinded to investigators and patients by necessity, as there is a distinct difference in size and appearance between the Precision Flow and HVT2.0 HVNI device designs. However, patients may not know the difference between conventional and new device design. This study is a crossover design trial that will measure, ventilation, comfort, and efficacy—specifically the effect of relief of dyspnea as demonstrated by RPD assessment and measured by TcPCO₂ device. In addition, patient physiologic outcomes (e.g. HR, RR, BP, SpO₂), as well as patient & clinician assessment scores will be evaluated and recorded. Figure 1 illustrates a flowchart of overall study procedures.

Screening, Enrollment, & Management

During screening, subjects will be asked to participate in this study, and if so, they will provide informed consent prior to enrollment. Subjects will be instructed that if at any time during the study that they wish to discontinue the study, they are free to stop the testing and discontinue study participation at any time. All study procedures will be explained to the subject prior to starting any procedures, and all participants will be given a copy of the informed consent form.

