Baseline Characterization will be performed just prior to the therapy acclimatization segment of this Phase. If, for any reason, the clinician does not deem the patient appropriate for the study, per inclusion/exclusion criteria, they may stop procedures during baseline characterization. Sitting down in a comfortable environment, the patient will be setup and prepared for the testing with appropriate data recording devices. The patient will be ON current/home oxygen therapy at this time (if applicable). While the subject is at rest, the following data will be collected (see Table 1): RR, HR, BP, SpO₂, tcPCO₂ and RPD (Modified Borg scale 0-10). For the RPD, the clinician will record patient scores.

Therapeutic Characterization will be performed immediately after the baseline segment is completed in Phase 2 only. Once the respiratory therapist or other clinician skilled in management of HVNI deems that the HVNI settings are having a therapeutic effect, the following data will be collected (see Table 1): RR, HR, BP, SpO₂, TcPCO₂ and RPD (Modified Borg scale 0-10). For the RPD, the clinician will record patient scores.

Patient & Clinician Perception Assessments will be performed by the clinician or therapist performing this phase's testing procedures. Immediately following the completion of this phase, the continuous Visual Analogue Scale (VAS) will be completed for each of the five endpoints for clinician assessment and the two endpoints for patient assessment. For patient perception these endpoints include: (1) relief of symptoms, and (2) comfort/tolerance. For clinician perception these endpoints include: (1) technical/clinical difficulties, (2) patient comfort & tolerance, (3) ease of use, (4) monitoring & support for therapy, and (5) expected/perceived patient outcomes.

Vapotherm, Inc
New HVNI Device Design Efficacy in Relieving Dyspnea
Confidential

Upon completion of Phase 2, the study testing procedures will be deemed completed, and any final study data will be recorded at this time. At this time, the patient may resume current/home oxygen therapy.

Other Medical Care

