- Clinician perception of Monitoring and support of therapy required (adjustments, refilling fluids, adjusting interface), ranging from Minimal to Frequent, as continuous VAS.

VIII. Statistical Analysis

Baseline patient demographics and characteristics will be summarized, compared, and appropriate statistical testing will be performed for the continuous and categorical variables. Assuming a non-normal data distribution for this crossover order-randomized study design, the non-parametric Wilcoxon Signed Rank Sum test will be performed with significance interval of 0.05 on all applicable variables. Parametric analytical analogues (e.g. t-test) will be use if the measurements present a normal distribution. Otherwise, for the categorical variables, the Fisher's Exact test will be performed. Data will be compared and graphed accordingly for a visual comparison with accompanied statistical notations.

IX. Risks and Discomforts

This validation study does not present significant risk to patients, as supplemental oxygen is routinely provided to patients as a standard practice in hospitals¹⁹. Use of high flow nasal cannula (HFNC) therapy has no known risks and has been used in clinical settings for approximately 17 years. Additionally, there are no known reports of adverse events related to the administration of high nasal flows when the gas has been appropriately conditioned to near body temperature and fully humidified. Existing literature indicates that approximately only 4 cmH₂O of distending pressure may be generated in the upper airway, which is well below any known threshold for injury.^{20,21} Furthermore, it has been demonstrated that delivery of high flows of conditioned gas from a nasal cannula has a positive effect on airway mucosal function.^{22,23} The patients enrolled in this study will be closely monitored as part of standard medical practice.

For these reasons, we have determined that this study represents non-significant risk to the subjects. The high flow nasal cannula system used has no known risk and has been used in hospitals for approximately 17 years. During both study phases, patients will be closely monitored as part of the normal care. Patients may experience mild discomfort from a cannula in contact with their nose, face or around their ears and possibly a runny nose from the humidity contained in the gas flow.

X. Potential Benefits

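### Section VIII plans no estimate of the relief each device gives, so similar RPD scores could be read as comparable relief when neither device lowered dyspnea

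*Combined protocol and SAP*

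**What the plan says.** The claim concerns relief. The hypothesis in Section II is that HVT2.0 "will deliver comparable ventilation and relief of patient dyspnea, when compared to the Precision Flow device in an inpatient or outpatient hospital setting". Aim 1 reads: "The primary endpoint is the patient's targeted relief of dyspnea, as measured by the modified Borg (rated perceived dyspnea [RPD]) for each device design tested". The same section adds that the endpoints "will establish equivalence of outcomes between Precision Flow HVNI and HVT2.0 HVNI device design".

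The analysis is generic. Section VIII says that "the non-parametric Wilcoxon Signed Rank Sum test will be performed with significance interval of 0.05 on all applicable variables", with a t-test if the data look normal. It names no change-from-baseline contrast, no relief threshold, no margin and no rule for declaring comparability.

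Section IV compares two active HVNI devices, with no untreated or sham phase. Section VI collects RPD at baseline and at Therapeutic Characterization in both phases, so relief can be computed. The state of the patient at those baselines varies:

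- **Phase 1:** baseline RPD may be recorded while the patient is already receiving HVNI.
- **Phase 2:** the patient is on current or home oxygen at baseline. No washout time is given, and the Phase 2 text recognises that some patients were on HVNI before the study.

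**The concern.** Comparable relief has two parts: relief occurred, and it was similar on the two devices. The plan addresses only the second. Similarity between two active treatments says something about relief only if the control lowered dyspnea in this trial.

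That cannot be taken for granted. Exposure is short: 5–10 minutes of acclimatization, then readings 5–10 minutes later. In Phase 2, characterization directly follows baseline. Entry requires only a Borg score of 3, which leaves some patients little room to improve. Both devices are meant to run at the same settings, which favours similar scores whether or not either device helps. What is at stake is whether the trial's main sentence can be interpreted.

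**Working it through.** **Inputs.** Section V gives the sample size by "using the paired t-test sample size calculation, with an expected difference of 2, and an expected standard deviation of 3", with 90% power and alpha 0.05. Of the SD it says "it was estimated that a value of 2 to 3 was suitable for the standard deviation of dyspnea for the modified Borg scale". These are inputs for a difference between devices. The documents give neither an expected fall from baseline nor its SD. Below, an SD of change of 2 to 3 is an assumption, and so is the ±2 margin.

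**1. The plan's own figure.** Power of the two-sided paired t-test = P(T > t₀.₉₇₅,ₙ₋₁), where T is noncentral t with n − 1 degrees of freedom and noncentrality δ√n/σ.

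- n = 26: 2√26/3 = 3.40, critical value 2.060, power 90.4%.
- n = 25: 2√25/3 = 3.33, critical value 2.064, power 89.2%.

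So 26 reproduces, and 26 × 1.2 = 31.2 gives the planned 32.

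**2. No relief on either device.** The true difference is 0, so the 0.05 test is non-significant in 1 − 0.05 = 95% of trials. Simulated integer Borg scores gave 94.8% to 95.6% for the Wilcoxon test at n = 26 or 32.

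**3. Would a margin cure it?** Take the rule that the 90% CI for the difference lies within ±m. At n = 26 and SD 3 the typical half-width is 1.708 × 3/√26 = 1.00. With a true difference of 0 the rule passes as follows:

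| Assumed margin | SD 2 | SD 3 |
|---|---|---|
| ±2 | 99.9% | about 90% |
| ±1 | about 60% | about 8% |

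**4. Why neither helps.** If both devices lower RPD by the same amount r, the difference is r − r = 0 for every r. The rates in steps 2 and 3 depend on the true difference and the SD, not on r. The device comparison therefore carries no information about r.

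**5. What a within-device estimate can show.** The chance that a 95% CI for the mean change shows a fall is:

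| Patients | True fall | SD 2 | SD 3 |
|---|---|---|---|
| 26 | 2 | 99.8% | 90.4% |
| 20 | 2 | 98.9% | 80.7% |
| 26 | 1 | 69% | 37% |

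For a true fall of 2, the relief wording is thus withheld in about 0.2% to 10% of trials with 26 patients and about 1% to 19% with 20.

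**6. Why baseline HVNI status matters.** Suppose that 25% are already on HVNI at baseline and show no further fall, while the rest fall by 2. The pooled mean fall is 0.75 × 2 = 1.5. At n = 26 the pooled interval shows a fall in about 92% of trials (SD 2) or 65% (SD 3). With 50% on HVNI the figures are about 59% and 34%.

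**7. Limit of the check.** If the mean change is truly zero, a fall is falsely shown in 2.5% of trials. Selection at Borg ≥ 3 can raise this through regression to the mean. The assumptions here are a true mean of 3 to 5, between-patient SD 1.5 to 2, within-patient SD 1 to 1.5, and the qualifying reading also serving as baseline. A device with no effect then shows a fall in roughly 5% to 40% of trials at n = 26.

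**The case against.** **The plan already looks for benefit.** Section VI makes relief of perceived dyspnea a titration target and takes readings once a clinician judges that the settings have a therapeutic effect. That is the nearest thing to a relief condition. But the judgement is unblinded, has no criterion, is not tied to Borg and does not enter the analysis. Section VII also records RPD at each segment, so change will be visible, though no conclusion depends on it.

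**The 95% is only 1 − alpha.** True, and it would be the same if both devices worked fully. That is step 4: the test cannot tell the two situations apart. The missing equivalence margin is a separate problem, and step 3 shows that supplying one does not resolve this one.

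**Stronger readings that the documents do not support.**

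- A reader might infer that the plan would declare two ineffective devices comparable. It states no rule for declaring comparability. The risk is that a non-significant result, or a later margin test, is read that way.
- A reader might infer that an off-HVNI baseline exists in each phase, so that a simple pass/fail test of relief is ready to use. Section VI allows HVNI at the Phase 1 baseline and does not exclude it in Phase 2. Step 6 shows that a test on all patients could fail although the device works.
- A reader might infer that a fall on Precision Flow proves that it worked. Without an untreated phase, regression to the mean and unblinded expectation can also produce a fall.
- A reader might take the difference of 2 and SD of 3 as the plan's inputs for relief. They are inputs for the between-device comparison.

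**Conclusion.** The point holds as a gap in analysis and interpretation. The stated sample size reproduces and is not in question. The hypothesis and primary endpoint are about relief, while Section VIII neither estimates relief within a device nor makes the conclusion depend on it. With no relief on either device, about 95% of trials would be non-significant. About 90% would satisfy a ±2 rule at n = 26 and SD 3, where that margin is assumed.

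The proposed check would lower the chance of wrongly using the relief wording to at most 2.5% if the mean change is truly zero. Under the assumptions of step 7 the bound is roughly 5% to 40%, before any expectation effect. This is a worthwhile, inexpensive improvement, and it changes what the trial may say rather than whether it can run.

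**What to change.** Add to Section VIII, with one CRF item:

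- **Baseline state.** Record whether the patient is on HVNI at each baseline RPD. Table 1 already lists treatment flow and oxygen at baseline, so this makes an existing item explicit. Section IV describes the Phase 2 switch as needing only a change of cannula, whereas Section VI describes a baseline on current or home oxygen. These passages must be reconciled so that the contrast has a defined meaning.
- **Estimate.** For each device, report the mean change in RPD from that phase's baseline to Therapeutic Characterization with a 95% CI. The main set is patients not on HVNI at that baseline. All patients, and Phase 1 only, are sensitivity analyses. Phase 1 alone gives about 13 per device, so a half-width of 2.179 × 2/√13 = 1.2 to 2.179 × 3/√13 = 1.8 points at SD 2 to 3.
- **Wording of the conclusion.** Use comparable relief only if the Precision Flow interval in the main set shows a fall. Otherwise conclude only on the similarity of RPD scores on the two devices.
- **Caveat.** State that an uncontrolled fall is necessary and not proof of efficacy, and name regression to the mean and unblinded expectation.

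No extra patients, visits or RPD readings are needed. The cost is that the relief wording is sometimes withheld when relief is real, at the rates in step 5. Those rates rise if true relief is below 2 points or if many patients are on HVNI at baseline. The equivalence margin still has to be specified separately.
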